2 STUDY DESIGN AND FLOW

Subjects who complete double-blind study treatment and the run-out period of the confirmatory study, and who are willing to participate, will be eligible to enter the ID-078A303 extension study.

The ID-078A303 study will be offered at every site participating in ID-078A301 and ID-078A302 (approximately 150 centers in 17 countries), and to every eligible subject.

[figure not shown]
Subjects assigned to the placebo arm in the confirmatory study will be randomized to receive either placebo or 25 mg ACT-541468 in a 1:1 ratio in the extension study. Treatment allocation will be stratified by age into 2 categories: < 65 and ≥ 65 years (the age entered at the screening visit of the confirmatory study will be taken into consideration for the randomization in the extension study).

Subjects assigned to one of the ACT-541468 arms in the confirmatory study will continue on the same dose (but assigned a new randomization number).

It was expected that approximately 1260 subjects (i.e., ~70% of the total subjects in the combined confirmatory studies) would enter the extension study after completing the

confirmatory study. The overall study design, including the transition from the confirmatory study, is depicted in [Figure 1](#).

Figure 1 Study design

.....> Monthly telephone call.

EODBT = end-of-double-blind treatment; EOS = End-of-Study; EOT = End-of-Treatment.

Subjects randomly assigned to the ACT-541468 arms in the confirmatory studies will receive the same dose in the extension study.

Subjects randomly assigned to the placebo arm in the confirmatory studies will be randomized to receive either placebo or 25 mg ACT-541468 in a 1:1 ratio in the extension study.

The study comprises 2 phases:

- The **double-blind treatment phase** starts when the treatment is allocated (Visit 1) and lasts 40 weeks, until the EODBT at Visit 5.
- The **safety follow-up phase** starts from the EODBT and ends 30 days after the last dose of double-blind study treatment with the EOS at Visit 7. It consists of the following two periods:
 - A single-blind placebo run-out period of 7 days (from the evening of Visit 5 until after all visit assessments have been performed at Visit 6 i.e., EOT).
 - A safety follow-up period (from EOT until EOS).

See Section 11.2 for a detailed definition of study periods.

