Observed values and change from baseline over time in sTST, sWASO, sLSO and IDSIQ scores (i.e., total score; alert/cognition, mood and sleepiness domain scores) will be summarized by age group at screening in the confirmatory study (< 65; ≥ 65 years) and overall using descriptive statistics.

A longitudinal data analysis method (i.e., linear mixed-effects model) will be used for the analysis of change from baseline in sTST, sWASO, sLSO and IDSIQ scores (i.e., total score; alert/cognition, mood and sleepiness domain scores), separately. All available data, regardless of occurrence of intercurrent events (e.g., study treatment discontinuation, the use of prohibited medication), will be included in the model. Subjects who are randomized (switched) from placebo to 25 mg in this study will be excluded from this longitudinal analysis as their exposure to treatment and timing of assessments are not aligned with the other treatment groups.

The analysis model will adjust for the baseline value of the relevant response variable (either sWASO, sLSO, sTST or IDSIQ scores), age group as per assigned strata (< 65; ≥ 65 years), treatment (10 mg; 25 mg; 50 mg; placebo), visit (Month 6 [Week 12]; Month 9 [Week 24]; Month 12 [Week 36]; as defined in [Table 6](#)), and the interaction of treatment by visit, and baseline by visit (SAS[®] code available in [Appendix 1](#)).

An unstructured covariance matrix, shared across treatment groups, will be used to model the correlation among repeated measurements. A restricted maximum likelihood approach will be used to derive (unbiased) estimates of variance components. The Kenward-Roger approximation will be used to compute the denominator degrees of freedom and adjust standard errors [[Kenward 1997](#)]. If this analysis fails to converge, the use of the heterogeneous Toeplitz covariance structure, shared across treatment groups, will be explored.

Appropriate contrasts will be used to test the treatment differences of interest (i.e., the difference in least squares [LS] mean change from baseline between ACT-541468 10 mg vs placebo, ACT-541468 25 mg vs placebo and ACT-541468 50 mg vs placebo at Month 6, Month 9 and Month 12, see [Appendix 1](#)). Month 6 is the mean value based on the sleep diary / IDSIQ entries performed at home over the 7 days in Week 12 of the extension study; Month 9 (Week 24) and Month 12 (Week 36) are defined similarly.

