The LS mean for each treatment group per time point will be displayed along with associated standard errors and 95% CIs. For each ACT-541468 dose level comparison with placebo, the placebo-adjusted LS mean will be displayed along with associated standard errors, 95% CI and unadjusted two-sided p-value.

Observed values and change from baseline over time in VAS scores, ISI[®], number of self-reported awakening, PGA-S and PGI-C will also be summarized using descriptive statistics.

Empirical cumulative distribution function plots of the observed cases of sWASO, sLSO, sTST and IDSIQ endpoints, separately, at Months 6, 9 and 12 for each treatment group will be provided. A summary will be provided showing the cumulative number and percentage of subjects meeting certain thresholds for sWASO, sLSO, sTST and IDSIQ endpoints, separately, for the observed range of values.

For sTST, sWASO, sLSO, each IDSIQ domain and total scores, VAS scores and number of self-reported awakenings, subjects must have at least 2 days of data during each week to calculate a weekly mean. Otherwise, the mean value will be considered missing for that week. The approaches above imply implicit imputation: the missing data points are given the same value as the mean of the non-missing data points of that same time point or week.

Subgroup analyses for sTST, sWASO, sLSO, each IDSIQ domain and total scores endpoints will be performed to investigate the consistency of the treatment effect (i.e., ACT-541468 vs placebo) across subgroups defined as:

- Age at screening of confirmatory study: $< 65, \geq 65$ years and $< 75, \geq 75$ years.

Specific subgroup analyses for sTST and each IDSIQ domain and total scores endpoints are defined below:

- Sex: Male, female.
- Region: US, other (non-US).
- BMI at screening of confirmatory study: $< 30, \geq 30$ kg/m².
- Race: White, Black or African American, Other*;

* The 'Other' category will not be considered for subgroup analyses due to the mix of races and small number of subjects limiting the ability (i.e., low power) to detect differences between treatment groups. 'Other' includes: American Indian or Alaska Native, Native Hawaiian or other Pacific Islander, Asian and Other (Entry for multiple races was to be reported under category 'Other'. Similarly, 'Not permitted as per legislation/regulation' was to be also grouped within this category 'Other').

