The same model as for the longitudinal analysis (i.e., linear mixed-effects model) will be fitted with the additional factor for subgroup, and the interaction of subgroup by treatment, subgroup by visit, and subgroup by treatment by visit. Subjects who are randomized (switched) from placebo to 25 mg in this study will be excluded from these longitudinal analyses.

Of note, age group will not be included as a covariate in the model of the subgroup analyses by age.

Treatment effect estimates (LS mean and associated 95% CI for the ACT-541468 comparison with placebo) at Month 6, 9 and 12 will be presented via forest plots.

At the time of interim analysis, treatment will still be ongoing for some subjects so the efficacy beyond 6 months should be interpreted with caution.

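### The age-group term is dropped from both age subgroup models, but it is redundant only at the 65-year cut; the < 75 contrasts lose adjustment for the mix of < 65 and 65–74 subjects

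*SAP*

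**What the plan says.** SAP Section 6.1 sets out the longitudinal model for sTST, sWASO, sLSO and the IDSIQ scores. Among its covariates is "age group as per assigned strata", with categories < 65 and ≥ 65 years.

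The same section defines age subgroups by age at confirmatory-study screening, at two cuts: 65 years and 75 years. Each subgroup model is the main model plus subgroup and its interactions with treatment, visit and treatment by visit. One exception follows: "age group will not be included as a covariate in the model of the subgroup analyses by age". It makes no distinction between the two cuts and gives no reason.

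On allocation, SAP Section 2 says: "Treatment allocation will be stratified by age into 2 categories: < 65 and ≥ 65 years". It also says who is randomized: "Subjects assigned to the placebo arm in the confirmatory study will be randomized to receive either placebo or 25 mg ACT-541468 in a 1:1 ratio". For everyone else, "Subjects assigned to one of the ACT-541468 arms in the confirmatory study will continue on the same dose". Subjects switched from placebo to 25 mg are left out of the longitudinal and subgroup models (Section 6.1).

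**The concern.** The exception makes sense at the 65-year cut, where subgroup and covariate are the same variable. Read as written, it also removes the covariate at the 75-year cut, where the < 75 group still contains two age strata. A programmer following the SAP would fit that model without the term.

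Two things are then at stake.

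- If the share aged 65–74 within < 75 differs between a dose arm and placebo, that difference goes straight into the contrast.
- The < 75 estimates rest on a different covariate set from the overall analysis and from the sex, region, BMI and race subgroups. The subgroup analyses are meant to show whether the treatment effect is consistent, so the models should not differ without a reason.

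**Working it through.** The plan gives no figure on this point, so there is none to reproduce. The check is structural first, then a sizing under stated assumptions.

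**1. Terms in each model (SAP Section 6.1)**

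| Model | < 65 / ≥ 65 age group | Subgroup factor and interactions |
|---|---|---|
| Main | kept | none |
| Sex, region, BMI, race | kept | yes |
| Age, cut at 65 | dropped | yes |
| Age, cut at 75 | dropped | yes |

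**2. Is the term redundant?** Take the fixed effects at one visit: intercept (1), treatment (3), subgroup (1), treatment by subgroup (3), age group (1). That is 9 columns. I used an illustrative data set with three age bands (< 65, 65–74, ≥ 75) spread over four arms.

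- Cut at 65: rank 8 of 9. The age-group column repeats the subgroup column. In the trial, only subjects whose assigned stratum differs from their screening age would break the identity.
- Cut at 75: rank 9 of 9. Age group varies within the < 75 cells, so it is not aliased.

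Everyone aged ≥ 75 is also ≥ 65, so the term is constant there, apart from any mis-stratified subjects. The loss concerns the < 75 contrasts only.

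**3. Precision.** Let *p* be the share aged 65–74 within < 75. Let *d* be the difference in change from baseline between 65–74 and < 65, in residual SD units. The documents give neither; I assume *p* = 0.2–0.4 and *d* = 0.1–0.5. With balanced arms, leaving the term out multiplies the SE by √(1 + *p*(1 − *p*)*d*²).

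- Low end: √(1 + 0.2 × 0.8 × 0.1²) = √1.0016, an increase of 0.08%.
- Middle: √(1 + 0.3 × 0.7 × 0.3²) = √1.0189, an increase of 0.94%.
- High end: √(1 + 0.4 × 0.6 × 0.5²) = √1.06, an increase of 2.96%.

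This treats < 75 on its own. The model pools the covariance with ≥ 75, where nothing is lost, so the real inflation would be slightly less.

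**4. Bias.** With an additive age effect, the unadjusted contrast shifts by *d* × (difference between arms in the 65–74 share).

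| Imbalance | *d* = 0.1 | *d* = 0.3 | *d* = 0.5 |
|---|---|---|---|
| 5 points | 0.005 SD | 0.015 SD | 0.025 SD |
| 10 points | 0.01 SD | 0.03 SD | 0.05 SD |

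To judge these imbalances, suppose (arm sizes assumed) 100 placebo and 200 dose subjects, with *p* = 0.3 and no balancing between arms. The chance SD of the difference in shares is √(0.3 × 0.7 × (1/100 + 1/200)) = 0.056. With 130 and 270 it is 0.049. Ten points is therefore about two chance SDs. Chance imbalance is already what the SE inflation describes, so the two sizes should not be added for it. Only a systematic difference, for example from selective roll-over, is bias beyond the SE.

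**5. Does keeping the term create a problem?** The < 65 / ≥ 75 cell is empty. The code in SAP Appendix 1 requests LS means without observed margins, so its default equal weighting would put half the weight for ≥ 75 on an age group with no such subjects. That shifts each ≥ 75 arm mean by *d*/2, or 0.05–0.25 SD under the same assumptions. The shift is the same in every arm and cancels in the treatment contrasts, which are what the forest plots show.

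**The case against.** The strongest case is that this is a prespecified and defensible simplification: one age dichotomy replaces another in a model about age. Several parts of it stand.

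- The 75-year model is not without age adjustment. It holds the 75-year factor with its interactions, plus baseline and baseline by visit. Only the residual difference between 65–74 and < 65 is lost.
- The 65-year subgroup analysis covers the same endpoints, and descriptive summaries by < 65 / ≥ 65 are planned, so a reader can see whether age 65 matters.
- The objective is exploratory (SAP Section 3.2), and no decision in the documents hangs on these estimates.
- Restoring the term is not quite free of side effects, because of the empty cell.

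A reader might also infer that the plan breaks the usual rule of adjusting for a factor used to stratify randomization. The documents do not support that for these contrasts. The extension's stratified 1:1 split applies to former placebo subjects, and the half that switched is excluded from the model. The dose arms are carried over from the confirmatory studies. So no modelled dose-versus-placebo contrast is randomized within the extension strata, and the documents supplied do not say whether the confirmatory randomization was stratified by age.

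That removes one argument for the term but leaves another. The same facts mean that extension randomization does not protect the age balance of these contrasts, and only about 70% of confirmatory-study subjects were expected to enter (SAP Section 2). Whether roll-over actually differed by age and arm is not known from the documents.

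**Conclusion.** The point holds as a minor one. The omission is justified at 65 years and has no stated reason at 75 years, where the term is estimable and is kept in the main and other subgroup models. The case for keeping it rests on possible age imbalance after roll-over and on consistent adjustment across the forest plots.

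The sizes in the working are small, and both the SE and the bias figures depend wholly on assumed values of *p*, *d* and the imbalance. They do not support a claim that any planned estimate is invalid or materially biased.

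**What to change.** Replace the note in SAP Section 6.1 with wording such as:

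> Age group (< 65; ≥ 65 years) is omitted only in the < 65 / ≥ 65 subgroup model. It is retained as an additive covariate in the < 75 / ≥ 75 subgroup model.

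Report treatment contrasts from the 75-year model. If arm-level LS means are shown, use observed margins taken within each age subgroup and common to all arms, so that ≥ 75 puts its weight on ≥ 65 and the arms stay comparable. If the sponsor prefers to leave the term out at 75 years, state the reason.

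The cost is one or two sentences and a small programming change. The covariate is already in the main model, so no new data are needed. SAP Section 10 applies all the SAP's analyses to the interim as well, so the wording is best settled before unblinded interim results are seen.

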7 SAFETY VARIABLES AND ANALYSES

7.1 Overview of safety analyses including subgroup analyses

Unless noted otherwise, the SS will be used for tables and listings of safety data. Safety data described below will be listed.

In the event of permanent study treatment discontinuation, it is recommended per protocol to perform the safety assessments of Visit 5 within 7 days of the last double-blind study treatment intake. Although some subjects may be considered as being off study treatment, the time from the last double-blind study treatment intake to the Visit 5 assessments is expected to be short. Therefore, for subjects who prematurely discontinue treatment, the safety data (laboratory tests, ECG, vital signs) measured within 7 days of the last double-blind study treatment intake will be included as being taken during double-blind study treatment. A subject who prematurely discontinues treatment may continue the planned study visits until EOS, without the run-out period. Therefore, for subjects who prematurely discontinue treatment, the safety data (laboratory tests, ECG, vital signs) measured more than 7 days from the last double-blind study treatment intake will be excluded from analyses.

Any unscheduled or re-test measurements will be excluded for determining last values during the double-blind treatment period. All scheduled, re-test and unscheduled measurements will be included for determining baseline values.

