## 2 RECOMMENDATIONS AND INSTRUCTIONS

### 2.1 Flexibility regarding site visits for subjects who can still go to sites

#### For subjects ongoing in ID-078A303:

- If the subject can travel to the investigator’s site, the investigator should:
  - Ensure the subject’s safety on his/her way to the site by following local/country regulations (e.g., not using public transportation). Alternatively, subjects can use taxis or private cars, the cost of which will be reimbursed by Idorsia.
  - Perform the on-site visit assessments according to the protocol.
  - An on-site visit is always preferable. Therefore, this may mean that the visit windows need to be extended, as long as the subject has enough study treatment. Study treatment can be delivered to the subject’s home, following the instructions as in Section 2.2. The reason for this delayed scheduled visit must be documented in the subject’s medical charts.

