7.2 Adverse events

Unless noted otherwise, the AE summary tables will include TEAEs occurring during the extension study i.e., AEs that started or worsened on or after double-blind study treatment start date of the extension study up to 30 days after double-blind study treatment end date. An AE that started or worsened during any unplanned double-blind study treatment interruption (e.g., due to AE) will be considered as treatment-emergent. In addition, an AE that started or worsened during a planned double-blind study treatment interruption (i.e., the run-out period or safety follow-up period) that falls in the treatment-emergent time window defined above, will be considered as treatment-emergent.

AEs will be coded using MedDRA. The MedDRA version used for reporting will be specified in the footnote of the applicable output.

The number and percentage of subjects experiencing a TEAE occurring during the extension study (including SAEs, AESIs after adjudication by the ISB, and AEs leading to premature discontinuation or temporary interruption of double-blind study treatment) will be summarized by SOC and/or PT, and/or maximum intensity.

Each AESI category (i.e., excessive daytime sleepiness, cataplexy, complex sleep behavior including hallucinations/sleep paralysis, suicide/self-injury, narcolepsy-like symptoms) will be summarized by PT separately.

A subject with multiple intensities reported for an AE will be summarized under the maximum intensity recorded for the event.

Apart from the summaries of occurrences, where each event is counted, a subject with multiple occurrences of an AE is counted only once in the AE category (e.g., SOC, PT). If a single AE worsens on the same treatment group, then this event will be considered as one occurrence.

AEs will be sorted by descending frequency, first in the ACT-541468 50 mg dose level, then in the ACT-541468 25 mg dose level, then in the ACT-541468 10 mg, then in the placebo treatment group, and finally in the ex-placebo/ACT-541468 25 mg. After this ordering, SOCs are presented in alphabetical order with PT sorted within SOC in alphabetical order.

The following AE summary tables will be provided:

- TEAEs,
- TEAEs during the double-blind study period^a,
- TEAEs occurring (i.e., that started or worsened) during the treatment withdrawal period (based on the TWS),
- TEAEs during the double-blind study period^a related to study treatment as assessed by the investigator and/or sponsor,

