7.4 Electrocardiography

Unless noted otherwise, ECG summaries and listings will include scheduled, re-test and unscheduled assessments.

Descriptive summary statistics for each scheduled visit (re-test excluded) will be provided for observed values and change from baseline (baseline as defined in Section 11.4) to Visit 3 (Week 14), Visit 4 (Week 27), Visit 5 (Week 40) and Visit 6 (Week 41) in ECG parameters (QT corrected according to Fridericia's formula, QT corrected according to Bazett's formula, heart rate, PR, and QRS).

Marked ECG abnormalities are defined in Table 5. The following summaries will be provided for each ECG parameter:

- Number and percentage of subjects having a marked ECG abnormality during the double-blind study period,
- Number and percentage of subjects having a marked ECG abnormality during the treatment withdrawal period (based on the TWS).

For the summaries above, percentages will be based on the number of subjects at risk: those having at least one post-baseline value in the study period under consideration per ECG parameter for criteria based on post-baseline values only, or those having a baseline value and at least one post-baseline value in the study period under consideration per ECG parameter for criteria based on change from baseline. For non-mutually exclusive criteria (i.e., HR < 45 bpm and < 50 bpm), a subject will be counted only once in the event of multiple occurrences but may be reported in more than one marked ECG abnormality criterion of a given parameter. For mutually exclusive criteria (e.g., HR and QTc), only the subject's worst post-baseline value (or worst change from baseline value) will be counted.

ECG findings during the double-blind study period and during the treatment withdrawal period (based on the TWS) will be summarized separately and listed.

ECG abnormality categories and findings will be sorted by descending frequency, first in the ACT-541468 50 mg dose level, then in the ACT-541468 25 mg dose level, then in the ACT-541468 10 mg, then in the placebo treatment group, and finally in the ex-placebo/ACT-541468 25 mg. After this sorting, ECG abnormality categories will be presented in alphabetical order with ECG finding sorted within ECG abnormality category in alphabetical order.

All ECG values for subjects with at least one marked ECG abnormality during double-blind study period or during the treatment withdrawal period will be listed.

Table 5 **Marked abnormalities in ECG parameters**

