11.2 Study periods

The enrollment period is defined as the time from the informed consent date until one day before double-blind study treatment start date.

The double-blind study period is defined as the time from the day of double-blind study treatment start until the day of EODBT (Visit 5) or for those who prematurely discontinued double-blind study treatment (i.e., those without an EODBT date), until one day after double-blind study treatment end date (if the treatment is taken before midnight), or the day of double-blind study treatment end date (if the treatment is taken after midnight). Time of treatment intake between 00:00 and 11:59 is considered as 'after midnight', while a time between 12:00 and 23:59 is considered as 'before midnight'. For any missing or incomplete time, it is presumed that the treatment was taken before midnight. For subjects lost to follow-up, the EOS date will be used as the end of DB study treatment. For subjects who complete double-blind study treatment with an interruption before continuing the run-out single-blind placebo treatment, the end of double-blind study period is the run-out

single-blind placebo treatment start date – 1 day. For subjects who prematurely discontinue treatment, the safety data (laboratory tests, ECG and vital signs) assessment up to 7 days after last drug intake are considered in the definition of double-blind study period [see Section 7.1].

For those subjects in the TWS, the treatment withdrawal period (or the run-out period) is defined as the time from one day after the end of the double-blind study period to the latter of seven days after the end of the double-blind study period or Visit 6 date. If the latter of the two dates falls after the EOS date, then the EOS date will be used.

The safety follow-up period is defined as the time from one day after the end of the treatment withdrawal period for those starting the treatment withdrawal period (i.e., subjects in the TWS) until the EOS date; or from one day after the end of double-blind study period for those not starting the treatment withdrawal period until the EOS date.

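### In premature discontinuers, a laboratory or ECG threshold crossing first seen more than 7 days after the last dose enters no laboratory or ECG summary table

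*SAP*

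**What the plan says.** SAP Section 7.1 treats laboratory, ECG and vital-sign values taken within 7 days of the last double-blind intake as on-treatment when a subject stops prematurely. Later values "measured more than 7 days from the last double-blind study treatment intake will be excluded from analyses". Section 11.2 builds the same rule into the study periods: safety data "assessment up to 7 days after last drug intake are considered in the definition of double-blind study period".

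The reason given is timing. Section 7.1 notes that "it is recommended per protocol to perform the safety assessments of Visit 5 within 7 days of the last double-blind study treatment intake" and expects the delay to be short. It adds that a subject who stops "may continue the planned study visits until EOS, without the run-out period".

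Other safety data follow other windows:

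- **Adverse events (Section 7.2).** By default, TEAEs count from the "double-blind study treatment start date of the extension study up to 30 days after double-blind study treatment end date". Deaths use the same 30 days. Under Sections 7.2 and 12.3, the tables of treatment-related, abuse-related and query-based TEAEs cover only the double-blind period. For early stoppers, Section 11.2 ends that period about one day after the last dose.
- **ECG (Section 7.4).** Marked abnormalities are counted in the double-blind period and, separately, in the treatment withdrawal period. The second count uses the Treatment Withdrawal Set, which under Section 4.1.4 requires at least one run-out placebo dose.
- **Listings.** Full laboratory data are listed for subjects with a marked abnormality during double-blind treatment (7.3). Full ECG data are listed for those with one in the double-blind or withdrawal period (7.4). Section 7.1 also states generally that safety data will be listed.

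**The concern.** Not calling a day-9 value on-treatment is reasonable. Giving it no place in any laboratory or ECG summary is a separate step, and the stated rationale does not justify that step. The rationale assumes that the stop visit happens within 7 days, but that timing is a recommendation, so some visits can fall later.

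The subjects concerned include any who stop because of an adverse effect. If a first abnormal liver value or QTc is found on day 8 or later, the threshold tables do not show it. If stopping or late attendance differs by dose, the loss also differs by arm. Long-term safety is the primary objective (SAP 3.1), and the interim report supports regulatory filings (SAP 10), so these tables matter.

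**Working it through.** The plan states no figure to reproduce here. The check sets the windows side by side, follows one hypothetical subject, and then looks at size.

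**1. Windows after the last double-blind dose, premature discontinuer**

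| Data | Counted until | Source |
|---|---|---|
| Laboratory, ECG, vital signs | day 7 | SAP 7.1, 11.2 |
| TEAEs (default) and deaths | day 30 | SAP 7.2 |
| Related, abuse and query-based TEAEs | about day 1 | SAP 7.2, 11.2, 12.3 |
| Withdrawal-period ECG | not eligible without a run-out dose | SAP 4.1.4, 7.4 |

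Subjects who do enter run-out have their ECGs tabulated up to the later of seven days after the double-blind period or Visit 6 (11.2).

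**2. One subject.** Suppose a subject stops before Week 14 and is first seen on day 9, with QTcF above 500 ms (a Table 5 criterion).

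- Double-blind ECG count: no, because 9 > 7.
- Withdrawal ECG count: no, because there was no run-out dose.
- Marked-abnormality listing: not triggered, because the finding lies in neither period.
- Main TEAE table: yes, if reported as an adverse event, because 9 ≤ 30.
- Related or query-based TEAE table: no, because that window closed about day 1.

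A first ALT above 3 × ULN on day 9 follows the same path through Section 7.3.

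**3. Denominators.** The ECG at-risk set needs a post-baseline value within the period considered (7.4). The first scheduled post-baseline ECG named is Week 14. The subject above, without an unscheduled ECG, may therefore have no counted value and leave the risk set. For laboratory tests, at risk means having at least one post-baseline value (7.3), and Section 11.5 takes post-baseline up to EOS. The text leaves open whether a late, excluded value keeps the subject in the laboratory denominator.

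**4. What a 30-day window would add.** Gap: 30 − 7 = 23 days, or 23/30 = 77% of the default TEAE window. Assume stopping is uniform between planned visits (assumption). Visits at Weeks 14, 27 and 40 are 13 × 7 = 91 days apart. The first interval is 14 × 7 = 98 days.

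| Next planned visit falls | 91-day gap | 98-day gap |
|---|---|---|
| within 7 days | 7/91 = 7.7% | 7/98 = 7.1% |
| days 8–30 | 23/91 = 25.3% | 23/98 = 23.5% |
| after day 30 | 61/91 = 67.0% | 68/98 = 69.4% |

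A 30-day window would reach about a quarter of next planned visits, plus any stop visit held on days 8–30.

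**5. Possible size.** Subjects with a late assessment = 1260 × d × s. Here 1260 is the expected enrolment (SAP 2), d is the share stopping early and s is the share of those assessed late. Neither d nor s is in the documents.

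- d = 10%, s = 10%: 12.6, about 13
- d = 20%, s = 25%: 63
- d = 40%, s = 50%: 252

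These are late assessments, not missed abnormalities.

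**The case against.** The strongest defence is that this is a pre-specified on-treatment rule with a stated reason, and that off-drug values would dilute on-treatment tables. That stands, and it is why the 7-day rule should remain for those tables. It does not explain why no supplementary table exists.

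A reader might infer more than the documents support:

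- **That late abnormalities disappear from safety reporting.** They do not. If reported as adverse events, they enter the default tables "up to 30 days after double-blind study treatment end date". The general listing sentence in 7.1 may also cover the underlying values.
- **That the laboratory window contradicts a uniform 30-day adverse-event window.** The 30 days are only the default. For several TEAE tables the window is about one day, shorter than the laboratory window.
- **That the combined liver criterion is missed when ALT is raised at Visit 3 and bilirubin two weeks later.** Section 7.3 requires both in one central laboratory sample, so two samples never qualify under any window. The Visit 3 ALT would already trigger the full laboratory listing.
- **That the COVID-19 addendum makes late stop visits likely.** Its remark in Section 2.1 that "this may mean that the visit windows need to be extended" is conditional on the subject having enough study treatment. It describes subjects still on drug and applies only to affected sites while affected.
- **That the run-out ECG table treats completers and early stoppers inconsistently.** That table serves the withdrawal assessment, and run-out ECGs are not added to the double-blind table either. The comparison shows only that an early stopper's off-drug ECG has no table of its own.
- **That vital signs lose threshold counts.** Section 7.5 plans no vital-sign threshold table.

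**Conclusion.** The point holds as a gap in reporting, not as an error in the on-treatment definition. In premature discontinuers, a laboratory or ECG threshold crossing first seen on day 8 or later appears in no laboratory or ECG summary table and does not trigger the marked-abnormality listings. Those who stop before Week 14 and are seen late may also have no counted post-baseline ECG value.

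The size is unknown, and the 13 to 252 range only shows how strongly it depends on assumed rates. A reader might want to quote a downward bias. For example, let f be the affected share, 0.10 × 0.20 = 2% to 0.30 × 0.50 = 15%, with abnormality rates of 8% in these subjects and 2% in the rest. The true rate would then be 0.02(1 − f) + 0.08f = 2.12% to 2.90%, against 2.0% shown. The documents do not support such a figure. Every input is assumed, and the calculation needs every affected subject to leave both numerator and denominator, whereas subjects with counted Week 14 or Week 27 values stay in. No difference between arms can be derived either.

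The protocol document available is the COVID-19 addendum, so what is sampled from discontinuers after the stop visit could not be checked. The change is a cheap improvement to the reporting of the primary objective.

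**What to change.** In SAP 7.1, 7.3, 7.4 and 11.2:

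1. Keep the 7-day rule for the on-treatment tables, means, changes and last values.
2. For Table 4, the elevated liver parameters (same-sample criterion unchanged) and Table 5, add a labelled supplementary count by treatment arm. It should include all collected values up to 30 days after the last double-blind intake.
3. Define the at-risk denominator for that count to match its window, which also settles the laboratory ambiguity.
4. Let the supplementary count trigger the laboratory and ECG subject listings.
5. Report by arm how many subjects and how many values the 7-day rule excludes.

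The cost is SAP wording and a few extra tables from values already in the database, with no new data collection. The supplementary counts will include some off-drug values, which the label should state. They will not reach planned visits after day 30, roughly two thirds of next planned visits under the uniform-stopping assumption. The exclusion counts in item 5 will show how much lies outside the 7-day rule.
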